8.4 Reporting of serious adverse events

Serious adverse events are not anticipated with either of the study drugs. However, if a study patient reports a serious adverse event, the study drug will be stopped, the event will be appropriately treated, and the adverse event form of the CRF will be completed. Information related to serious adverse events must also be recorded on the Serious Adverse Drug Experience Report Form separate from the information in the CRF. Bayer AG, the study monitor, and the Ethical Review Committee of the ICDDR,B must be notified of an adverse event occurrence within 24 hours by the investigators.

The Serious Adverse Event Report must be sent directly to the **AE Management Team in Germany, [contact].**

The Local Drug Safety Monitor's details are as follows:

[name]
Bayer (Singapore) Pte Ltd
[name]
[name]
[contact] ([name] [name])
[contact]
E-mail: [contact]

Adverse events and serious adverse events occurring during the trial are to be followed up until resolved or until no change in the patient's condition is expected. Adverse events or serious adverse events noted during the follow-up phase (Week 4 - 6) are to be reported and followed up as applicable.

9. Statistics

9.1 Sample size estimation

The primary efficacy variable is the clinical response of the patient. The aim of the study is to show that single-dose therapy with ciprofloxacin oral suspension (test treatment) is at least as effective as the 3-day treatment regimen with erythromycin. The anticipated cure rate for ciprofloxacin is at least 0.85, and for erythromycin at most 0.80. The statistical hypothesis and alternative are:

$$H_0 : P_T - P_R < -0.15$$

$$H_a : P_T - P_R \geq -0.15$$

Rejection of the hypothesis allows one to conclude that the cure rate P_T for the test treatment is at most 15% less than the cure rate P_R of the reference treatment.

Given these assumptions and hypotheses, a power of 90%, and a two-sided significance level of 5%, a sample size of $N = 80$ patients per group are required to reject the above hypothesis (Farrington CP, Manning G. Statistics in Medicine 1990: 1447-1454). Assuming an invalidity rate of 10%, a total sample size of 180 patients is required.

Pharmacokinetics

The first 20 patients aged 2 to 5 years and the first 20 patients, aged > 5 years who enter the study will be evaluated for PK.

9.2 Data management

All relevant study data will be entered into a computer using data management software (Clintrial 4.1). Data will be entered twice to ensure accuracy of data entry. Standard Bayer and study specific edit checks will be programmed for the data.

All data discrepancies and queries will be referred to the study centres, and an audit trail of all data corrections and updates will be maintained.

9.3 Disposition of patients / Enrolment characteristics

Adherence to the study protocol will be checked and all deviations from the study protocol, including withdrawals, will be documented. The number and frequency of protocol violations and withdrawals will be presented by treatment group. Demographic and baseline characteristics will be summarised by treatment group. Continuous data will be summarised by descriptive statistics (N, mean, median, standard deviation, minimum and maximum, and interquartiles) and categorical data by means of absolute and relative frequencies.

The comparability between the two treatment groups regarding demographic and baseline data will be assessed. Continuous variables will be compared by Student's t test. Categorical variables will be compared by the chi square test or Fisher's exact test when appropriate.

9.4 Efficacy analysis

The efficacy variables (clinical and bacteriological response at test of cure visit) will be listed for all patients. The two treatment groups will be compared by calculating the Mantel-Haenszel point estimate and 95% confidence interval for the difference in success rates (clinical and bacteriological). For the single dose treatment with ciprofloxacin oral suspension to be declared at least as effective as the 3-day treatment with erythromycin oral suspension the lower bound of the 95% CI for the difference in clinical success rate at test of cure must be ≥ -0.15 (-15%).

The secondary efficacy variables will be listed for each patient, with descriptive statistics for each treatment group. With regard to duration of diarrhoea, the treatments will be compared using the log-rank test, and Kaplan-Meier curves will be presented, if appropriate, otherwise the data will be analysed descriptively using median duration. The stool and vomit volumes, proportion of patients requiring unscheduled intravenous fluids, and frequency of vomiting will be compared descriptively.

9.5 Safety analysis

All safety variables will be analysed descriptively. Adverse events will be listed with detailed descriptions. Adverse events will be summarised by frequencies, the number of patients and percentage of patients according to body system categories.

The individual laboratory variables will be listed, with summary statistics for each treatment group. The frequencies of abnormal laboratory values will be given for each treatment group. All the other safety variables will be listed and summarised by means of summary statistics or relative and absolute frequencies.

9.6. Pharmacokinetic analysis

Ciprofloxacin concentrations will be determined in the first 20 patients, aged 2-5 years, and in the first 20 patients, aged > 5 years who will enter the study. Ciprofloxacin concentrations will also be determined in all patients who vomit within 30 minutes of receiving their first dose of medication.

Ciprofloxacin concentrations will be determined on both stool and serum. Stool will be collected in six-hourly for the first 72 hour of the study (thus 12 stool samples per patient). Concentrations will be determined using a HPLC-method. Concentrations will be determined on both uncentrifuged and centrifuged supernatant samples, to determine how much of the drug will be protein bound.

A population pharmacokinetic model will be used to determine pharmacokinetics in blood. Blood samples will be taken from each patient during one of four time periods; before drug administration; within 1 hour of first drug administration; 1-2 hours after first drug administration; and 4-12 hours after the first dose. A 1-ml sample will be required at each time window.

Erythromycin concentrations will be determined only in stool, which is the active site of infection. Erythromycin concentrations will also be done on six-hour aliquots, and determinations will be done using a bioassay method.

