- **Bacteriological success:** eradication of the infecting *V. cholerae* organism from faecal specimens within 48 hours of initiation of the study drug without its subsequent isolation by Day 5.
- **Bacteriological failure:** isolation of infective *V. cholerae* O1 or O139 from a faecal sample on Days 3, 4 or 5.

Pharmacokinetic criteria

- **Pharmacokinetics:** ciprofloxacin concentrations will be determined for both stool and serum.
 - To determine the pharmacokinetics of ciprofloxacin, blood samples will be taken from each patient during one of four time periods; before drug administration; within 1 hour of first drug administration; 1-2 hours after first drug administration; and 4-12 hours after the first dose. A 1-ml sample will be required at each collection time.
 - Stool will be collected 6-hourly for the first 72 hours of the study (thus 12 stool samples per patient).
 - Concentrations will be determined using the HPLC-method. Concentrations will be determined on both uncentrifuged and centrifuged supernatant samples, to determine how much of the drug is protein bound.
 - Erythromycin concentrations will be determined only in stool, which is the active site of infection.

Description of subject groups for analysis

Pharmacokinetic population

Ciprofloxacin concentrations will be determined in the first 20 patients aged 2-5 years, and in the first 20 patients, aged > 5 years who will enter the study. Ciprofloxacin concentrations will also be determined in all patients who vomit within 30 minutes of receiving their first dose of medication.

Safety analysis population

Patients will be included in the safety analysis if they receive at least one dose of study treatment.

ITT analysis population

Patients will be included in the ITT analysis if they have been diagnosed with cholera due to *V. cholerae* O1 or O139, and if they have received at least one dose of study treatment. Patients regarded as treatment failures (as discussed above) will be included in the ITT analysis.

PP analysis population

Patients will be included in the PP analysis if they satisfy the criteria for a valid course. Patients regarded as treatment failures (continuation of watery stool for > 48 hours) will be included in the PP analysis.

Definition of a valid course

For a course of therapy to be valid for evaluating the efficacy of treatment, the following criteria must be met and documented in the CRF:

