 - To determine the pharmacokinetics of ciprofloxacin, blood samples will be taken from each patient during one of four time periods; before drug administration; within 1 hour of first drug administration; 1-2 hours after first drug administration; and 4-12 hours after the first dose. A 3-ml blood sample (sufficient to yield 1 ml of plasma) will be drawn at each collection time.
 - Stool will be collected 6-hourly for the first 72 hours of the study (thus 12 stool samples per patient).
 - Concentrations will be determined using the HPLC-method. Concentrations will be determined on both uncentrifuged and centrifuged supernatant samples, to determine how much of the drug is protein bound.
 - Erythromycin concentrations will be determined only in stool, which is the active site of infection.

The analysis will be conducted by [name], Bayer. Samples will be transported to the Bayer laboratory in Germany.

Instructions for transporting ciprofloxacin blood samples for the PK evaluation are as follows:

- Protect samples during all steps from direct sunlight.
- Blood samples should be drawn into NH₄-heparin tubes.
- Blood, adequate to produce 1 ml of plasma should be drawn at each sampling time (e.g. a 3-ml blood sample, sufficient to yield 1 ml of plasma).
- Up to 2 hours after sampling, the blood should be centrifuged for 10 minutes at 2000 g and +20°C. The plasma must then be separated and transferred into appropriately labelled tubes (glass, polystyrene, or polypropylene).
- Samples should be stored at about -20°C and shipped on dry ice.
- Analyses must be performed within 24 months.

- **Urinalysis:** urine specimen will be tested for pH, protein, ketones, blood and glucose. General appearance will be determined, and microscopic examinations will be done for cells, casts and crystals. This will be done before initiation of the study drugs on the day of admission and on Day 5. Any casts or crystals will be described in detail.

Note: A flow chart of required tests and observations is presented in Appendix 12.1.1 and a clinical examination of joint functions is presented in Appendix 12.1.2.

Case Management

Clinical evaluation and laboratory studies

Patients will be hospitalised for at least 5 days. The following clinical evaluations will be performed on study patients:

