1.1 Pharmacokinetics criteria, (Protocol Outline, page 10)

Before Revision:

- **Pharmacokinetics:** ciprofloxacin concentrations will be determined for both stool and serum.
 - To determine the pharmacokinetics of ciprofloxacin, **blood samples will be taken** from each patient during one of four time periods; before drug administration; within 1 hour of first drug administration; 1-2 hours after first drug administration; and 4-12 hours after the first dose. **A 1-ml sample will be required at each collection time.**
 - Stool will be collected 6-hourly for the first 72 hours of the study (thus 12 stool samples per patient).
 - Concentrations will be determined using the HPLC-method. **Concentrations will be determined on both uncentrifuged and centrifuged supernatant samples, to determine how much of the drug is protein bound.**
 - Erythromycin concentrations will be determined only in stool, which is the active site of infection.

After Revision:

- **Pharmacokinetics:** ciprofloxacin concentrations will be determined for both stool and serum.
 - To determine the pharmacokinetics of ciprofloxacin, **3.0 ml of blood will be taken from each patient during one of the following four time periods;**
 - 1. before drug administration,**
 - 2. within 1 hour of first drug administration,**
 - 3. 1-2 hours after first drug administration and**
 - 4. 4-12 hours after the first dose.**
 - Stool will be collected 6-hourly for the first 72 hours of the study (thus 12 stool samples per patient).
 - Concentrations will be determined using the HPLC-method.
 - Erythromycin concentrations will be determined only in stool, which is the active site of infection.

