1.3 Secondary Outcome Measures, (Section 5.10.2, page 33)

Before Revision:

Ciprofloxacin concentrations will be determined for both stool and serum. Stool will be collected in six-hourly for the first 72 hour of the study (thus 12 stool samples per patient). **Blood samples will be taken** from each patient during one of four time periods; before drug administration; within 1 hour of first drug administration; 1-2 hours after first drug administration; and 4-12 hours after the first dose. **A 1-ml sample will be required at each time window.**

After Revision:

Ciprofloxacin concentrations will be determined for both stool and serum. Stool will be collected in six-hourly for the first 72 hour of the study (thus 12 stool samples per patient). **3.0 ml of blood will be taken from each patient during one of the following four time periods;**

1. before drug administration,
2. within 1 hour of first drug administration,
3. 1-2 hours after first drug administration and
4. 4-12 hours after the first dose.

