1.4 Pharmacokinetic Analysis, (Section 9.6, page 45)

Before Revision:

A population pharmacokinetic model will be used to determine pharmacokinetics in blood. **Blood samples will be taken** from each patient during one of four time periods; before drug administration; within 1 hour of first drug administration; 1-2 hours after first drug administration; and 4-12 hours after the first dose. **A 1-ml sample will be required at each time window.**

After Revision:

A population pharmacokinetic model will be used to determine pharmacokinetics in blood. **3.0 ml of blood will be taken from each patient during one of the following four time periods;**

1. before drug administration,
2. within 1 hour of first drug administration,
3. 1-2 hours after first drug administration and
4. 4-12 hours after the first dose.

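### Section 9.6 still reads an unspun-versus-spun comparison as protein binding, which it cannot show; the amendment removed this step from the outline and section 5.6.1 but not from here

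*Protocol*

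**What the plan says.** Section 9.6 has a paragraph that opens by naming stool and serum, goes on to six-hourly stool collection and the HPLC assay, and ends with: "Concentrations will be determined on both uncentrifuged and centrifuged supernatant samples, to determine how much of the drug will be protein bound". The version 10 body carries nearly the same sentence in the Protocol outline (Pharmacokinetic criteria) and in section 5.6.1: "Concentrations will be determined on both uncentrifuged and centrifuged supernatant samples, to determine how much of the drug is protein bound".

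The amendment on the strategy for pharmacokinetic blood sampling revises both of those places. In its After Revision text for the outline (item 1.1) and for section 5.6.1 (item 1.2), the assay bullet is reduced to "Concentrations will be determined using the HPLC-method". For section 9.6 (item 1.4), the Before and After text cover only the paragraph that begins "A population pharmacokinetic model will be used to determine pharmacokinetics in blood". The paragraph holding the protein-binding sentence is neither shown nor changed.

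The only spin conditions in the document are in the handling instructions for blood samples in section 5.6.1: "the blood should be centrifuged for 10 minutes at 2000 g and +20°C", after which the plasma is separated off.

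**The concern.** Section 9.6 fixes both a laboratory contrast and what that contrast is to mean, and the two do not match. Spinning a sample divides it into solids and liquid. Protein-bound and free drug are both in the liquid, so assaying the liquid does not tell them apart. Followed as written, section 9.6 would put a protein-binding label on a quantity that measures something else.

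The second difficulty is consistency. The amendment marks the sentence as changed and omits it in two places. Section 9.6 is also on its list of sections to revise, yet the sentence stays there. After amendment, the section that governs the analysis asks for a result that the section describing the laboratory work no longer mentions.

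At stake is the accuracy of one descriptive pharmacokinetic result. Pharmacokinetics is trial objective (iii), and the protocol regards stool as the place where the infection is active, so a mislabelled fraction there is worth correcting even though no test or decision depends on it.

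**Working it through.** The plan gives no figure to reproduce. The check has three parts.

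**1. What the contrast estimates.** Take the drug in an unspun sample as 1. Let s be the share held on or in solids, and p the share of the dissolved drug that is bound to dissolved protein. Express both measurements per unit of whole sample, ignoring the volume taken up by the solids.

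- Unspun sample: 1 = s + (1 − s).
- Supernatant after an ordinary spin: 1 − s, made up of protein-bound drug p(1 − s) and free drug (1 − p)(1 − s).
- Reported share: (unspun − supernatant) / unspun = [1 − (1 − s)] / 1 = s.
- Share actually bound to dissolved protein: p(1 − s).

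The reported share does not contain p. Two illustrations, with values chosen only to show the mechanism:

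| s | p | Reported as bound | Actually bound to dissolved protein |
|---|---|---|---|
| 0.6 | 0 | 60% | 0 × 0.4 = 0% |
| 0 | 0.4 | 0% | 0.4 × 1 = 40% |

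The documents give neither s nor p, so the likely size of the error is unknown.

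**2. Whether an ordinary spin could remove dissolved protein.** This is a plausibility check using the one spin the document gives, 2000 g for 10 minutes. That spin prepares plasma from blood and is not presented as the binding step.

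- Acceleration: 2000 × 9.81 = 19,620 m/s².
- Time: 10 × 60 = 600 s.
- Distance moved = sedimentation coefficient × acceleration × time.
- Assumption, not in the documents: 4 to 20 S for dissolved protein (1 S = 10⁻¹³ s).
- At 4 S: 4 × 10⁻¹³ × 19,620 × 600 = 4.7 × 10⁻⁶ m, about 4.7 micrometres.
- At 20 S: about 23.5 micrometres.
- In an assumed 10 mm column, 23.5 micrometres is 0.235% of the depth. Clearing the column would need 0.01 / (19,620 × 600) = 8.5 × 10⁻¹⁰ s, about 8,500 S, which is far above the assumed range.

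Dissolved protein stays in the liquid under such a spin. No filtration, dialysis or ultracentrifugation step is described anywhere in the document.

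**3. Where the sentence stands after amendment.**

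| Place | Version 10 body | Amendment | After amendment |
|---|---|---|---|
| Outline, Pharmacokinetic criteria | present | item 1.1 omits it | gone |
| Section 5.6.1 | present | item 1.2 omits it | gone |
| Section 5.10.2 | never present | item 1.3, not applicable | none |
| Section 9.6 | present | item 1.4 changes another paragraph | still present |

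Count: 3 − 2 = 1 occurrence left, in section 9.6. The bound-in body still prints the sentence in the outline and section 5.6.1 because it is the unconsolidated version 10. That is not an error. The comparison that matters is between the amended section 5.6.1 and the unamended paragraph of section 9.6.

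**The case against.** The strongest reply is that this is a leftover sentence with little consequence. No planned analysis uses a bound fraction, and neither the objectives nor the outcome lists mention protein binding. The population model concerns blood concentrations. The step has already been taken out of the section that describes the laboratory work, so it may never be carried out. Stool spin conditions are not given and may sit in a laboratory manual, and the plasma spin is only a preparation for shipping. All of this stands, and it limits the weight of the point. It does not rescue the sentence, because section 9.6 itself states what the contrast is for, and an ordinary spin cannot serve that purpose.

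A reader might infer three stronger things that the documents do not support.

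- **That the laboratory has contradictory orders, one assay per sample against two.** The amended section 5.6.1 names the HPLC method and sets no number of assays. It is silent; it does not forbid the paired assay.
- **That deletion would save about 480 assays.** That figure is 40 children × 12 stool samples = 480, doubled to 960 by pairing. It assumes that all 40 children received ciprofloxacin. The protocol takes the first 20 entrants in each of two age bands without restricting them to one arm. With an even split, about 20 × 12 = 240 samples would be involved. Children who vomit early are added to the set in unknown number. No firm count follows.
- **That the remainder would be reported as free, active drug.** Nothing in the protocol says so.

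**Conclusion.** The point holds as a minor one. Section 9.6 states an interpretation that its own measurement cannot support, and the amendment left that sentence in place while removing it from the outline and section 5.6.1. The method part assumes an ordinary spin for stool, since the conditions are not stated; only a separation step that the protocol does not describe would change it. The amendment part rests on the text alone.

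The paired assay is not without value: it would show drug associated with stool solids, and only the label is wrong. The size of any mislabelling cannot be given from the documents, and the percentages in the working are illustrations. The effect is confined to one secondary pharmacokinetic description. Total stool and serum concentrations, the primary endpoint, the sample size, the non-inferiority comparison and safety are unaffected.

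**What to change.** Delete the protein-binding sentence from section 9.6, so that it agrees with the amended outline and section 5.6.1. If the sponsor wishes to keep the paired stool assay, say so in sections 5.6.1 and 9.6 alike, describe the difference as drug associated with stool solids and the supernatant value as dissolved (not free) drug, and make no statement about protein binding.

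Either change is a sentence or two in an amendment. Deletion needs no new samples, and neither change alters the sample size or any efficacy or safety analysis.

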12.1 Trial flow chart

ICDDR,B LIBRARY
DHAKA 1212

RECEIVED 1 0 OCT 2004

A-040649

12.1.1 Trial flow chart

Appendix 12.1.1
Flow chart for study activities

Assessments	Time										
	Initial Screening	Rehy- dration Period*	After Rehy- dration Period**	Observation Period	D-1	D-2	D-3	D-4	D-5	10 to 14 Days Follow-up (after study entry)	4 to 6 Weeks Follow-up (after study entry)
Inclusion/exclusion criteria	X										
Medical history ¹	X										
Demographics ²	X										
Physical examination ³	X			X	X	X	X	X	X	X	X
Intake/output (stool, urine, vomitus)		X		X	X	X	X	X	X		
Examination of joint ⁴	X				X	X	X	X	X	X	X
Faecal cultures ⁵	X						X			X	X
Rectal swab ⁶	X				X	X	X	X	X	X	X
Antimicrobial cultures ⁷	X										
Susceptibility testing and MIC ⁸	X										
Microscopic examination of stool ⁹	X							X			
Haematology ¹⁰	X								X		
Clinical chemistry ¹¹	X								X		
Urinalysis ¹²	X								X		
Pharmacokinetics (stool and serum)					X	X	X				
Start of study medication ¹³					X						
Clinical response ¹⁴									X		
Bacteriological response ¹⁵									X		
Adverse events											

Note: ¹ = Current illnesses and underlying diseases and medication, surgical procedures, previous joint problems, previous use of quinolones and, if known, date of onset of underlying diseases.
² = Sex, race, age.

- 3 = Weight, temperature, pulse/heart rate, respiratory rate, abdominal signs and symptoms, determination of hydration status and rehydration according to WHO guidelines.
- 4 = Ankles, knees, hips, wrists, elbows and shoulders for pain and inflammation.
- 5 = Stool culture for enteric pathogens (*V.cholerae*, *Salmonella*, *Shigella* and *Campylobacter*).
- 6 = For the isolation of *V.cholerae* 01 and 0139.
- 7 = For *V.cholerae* and other enteric pathogens isolated from the specimens collected before initiation of drug therapy. Susceptibility to tetracycline, trimethoprim-sulfamethoxazole, chloramphenicol, erythromycin, furazolidone and ciprofloxacin.
- 8 = For tetracycline, trimethoprim-sulfamethoxazole, chloramphenicol, erythromycin, furazolidone and ciprofloxacin.
- 9 = For semi-quantitative assessment of presence of leukocytes and erythrocytes, and demonstration of haematophagous trophozoites of *E. histolytica* and other parasites.
- 10 = Haematocrit, total and differential (neutrophils, lymphocytes, monocytes, eosinophils, basophils) white blood cell counts, and platelet count.
- 11 = Serum sodium, chloride, potassium, bicarbonate, creatinine, bilirubin, AST, ALT and alkaline phosphatase. (If the baseline creatinine is > 200 mcmmol/L, any patient with creatinine > than 200 mcmmol/L 24-hour post-administration, will be considered as suffering from renal failure and will be withdrawn from the trial.)
- 12 = pH, protein, ketones, blood and glucose; microscopic examinations will be done for cells, casts and crystals.
- 13 = After 4-hour observation period. Study days will be counted from the time of administration of the first dose of the study drugs, and each 24-hour period will constitute a study day.
- 14 = Clinical response includes the following: Weight, History and physical examination, Vital signs, Fluid therapy, Quantitation of stool volume, Feeding, X-ray and MRI.
- Weight: Before rehydration (dehydrated weight), after rehydration (rehydration weight) and just before administration of the study drug (after the 4-hour observation period), and at 24 hour intervals from the time of administration of the first dose of the study drug during hospitalisation.
- Physical examination: before rehydration, after rehydration, at the time of administration of the study drug, and then daily during hospitalisation. Physical examinations will also focus on adverse events including vomiting, gastrointestinal distress, rash, and joint assessment.
- Vital signs: pulse and respiratory rates, and blood pressure will be recorded before rehydration, after rehydration, just before administration of study drug, and then every 6 hours during the study.
- Quantitation of stool volume: Also for each 6-hour period during the study.

- = Rehydration guidelines according to WHO guidelines. Children admitted with severe dehydration according to the WHO guidelines will be given 100 ml/kg of Dhaka Solution over 3-4 hours. After initial rehydration, children will be evaluated and appropriate treatment plan will be used for continuation of further fluid therapy.
Fluids given to maintain hydration should be based on the amount of ongoing stool losses as well as the child's willingness to drink. Fluid therapy will continue until diarrhoea stops. If signs of dehydration reappear, fluid appropriate to the degree of dehydration will be administered and the study protocol will continue to be followed.
- = Appropriate feeds for age will be provided.
Radiological examination of the affected joints and, as appropriate, ultrasonographic and magnetic resonance imaging (MRI) examination of the affected joints and/or joint fluid assessments will be performed.
- 15 = For evaluation of bacteriological response to the treatment regimen, stool or rectal swab culture will be done on each day of the study for isolation and identification of *V cholerae* O1 or O139.

